**6.0 STUDY SYNOPSIS**

Title	An Open Label Phase 1b/2 Study of Orally Administered PLX3397 in Combination with Radiation Therapy and Temozolomide in Patients With Newly Diagnosed Glioblastoma																																
Study Objective(s)	The study objectives are to assess the potential for PLX3397 to improve the efficacy of standard of care radiation therapy (RT) + temozolomide (TMZ) in patients with newly diagnosed glioblastoma (GBM). For Phase 1b dose escalation, the primary objective is identification of the recommended Phase 2 dose (RP2D). For Phase 2, the primary objective is the comparison of median Progression Free Survival (PFS) to a historical control. Secondary objectives include the evaluation of overall survival (OS), pharmacokinetics (PK), correlative imaging studies, safety, and exploratory endpoints of pharmacodynamic (PD) effects of PLX3397.																																

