## 10.0 DESIGN

### 10.1 Description

This will be an open label, uncontrolled Phase 1b/2 trial in patients with newly diagnosed GBM who have recovered from complete or partial surgical resection. All patients will be treated with PLX3397 in addition to standard-of-care combination radiation therapy (RT) plus temozolomide (TMZ) followed by adjuvant TMZ. During Phase 1b dose escalation, two PLX3397 administration schedules, 7 days/week vs. 5 days/week (M-F) will be explored. During Phase 2, patients will be treated with the RP2D.

There are 4 sequential periods: 1-week PLX3397 monotherapy; 6-week PLX3397/RT/TMZ combination therapy; 4-week recovery; and, PLX3397/TMZ adjuvant therapy. PLX3397 will be administered twice daily either 7 days/week or 5 days/week (Monday through Friday) starting 1 week prior to the initiation of RT and will continue twice daily either 7 days/week or 5 days/week (Monday through Friday) during the 6-week course of RT.

Phase 1b PLX3397 dose and schedule cohorts are shown in [Table 2](#).

A detailed Trial Flow Chart is available in [Section 6.0](#), and procedures by study day are provided in [Section 13.0](#).

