#### **10.5 Duration of Study**

The duration of the Phase 1b portion of the study will depend on the number of cohorts required and the need for replacement patients. For the Phase 2 portion of the study, a recruitment rate of 1 patient per site per month is anticipated. The total duration of enrollment is expected to be approximately 18 months. The duration of follow-up will depend on the prolongation of the median PFS; the study is powered to detect a median PFS of approximately 8 months.

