### **21.2 Sample Size and Power**

For the primary endpoint of median PFS, based on a one-sided log rank test with a significance level of 0.1 and power of 80%, 22 events (death or progression) in approximately 31 patients would be required to detect a 50% relative hazard reduction in progression-free survival due to the addition of PLX3397 compared to the recent historical control median PFS of 5.5 months (RTOG 0525). Assuming a ~30% rate of non-evaluability, approximately 37 patients are planned to be enrolled in the Phase 2 portion of the study, which when combined with the 7 patients treated at that dose level in the Phase 1 portion of the study will yield approximately 44 patients.

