#### 21.4 Efficacy Analysis

Response to treatment will be evaluated using the Response Assessment in Neuro-Oncology (RANO) criteria (Wen 2010). The response criteria are summarized in Attachment 3. All patients who are eligible for efficacy analyses will be evaluable for PFS, calculated for each subject as the number of days from the first day of treatment (C1D1) to the date of the first documented disease progression or date of death, whichever occurs first. The Kaplan-Meier method will be used to estimate the median PFS.

Statistical modeling will be used to match the experimental group to the RTOG 0525 historical group for expected prognosis based on both clinical and molecular factors, importantly the level of MGMT methylation in the tumor tissue.

For each subject with a response to therapy, duration of response will be calculated. The duration of response is defined as number of days from the date of initial response to the date of first documented disease progression or death, whichever occurs first. The Kaplan-Meier method will be used to estimate median duration of response. In the event no disease progression or death is documented prior to study termination, analysis cutoff, or the start of confounding anticancer therapy, PFS and duration of response will be censored at the date of last evaluable tumor assessments. The median duration will be compared to the historical control PFS of 5.5 months. The secondary endpoint of OS will be analyzed in a similar fashion.

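### The log-rank test that supports the 80% power in 21.2 is missing from the analysis section: 21.4 gives a Kaplan-Meier median and a 5.5-month benchmark but no primary test or decision rule

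*Combined protocol and SAP*

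**What the plan says.** The sample-size text (21.2, repeated in the synopsis under Statistical Considerations) is the only place that names a test. The calculation is "based on a one-sided log rank test with a significance level of 0.1 and power of 80" percent. It states that "22 events (death or progression) in approximately 31 patients would be required" and that the aim is "to detect a 50% relative hazard reduction in progression-free survival due to the addition of PLX3397", against a historical median PFS of 5.5 months from RTOG 0525.

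The other sections do not mention that test:

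- **Objectives (synopsis, 9.0 and 21.1.2).** For Phase 2, "the primary objective is the comparison of median Progression Free Survival (PFS) to" a historical control. The primary endpoint in the synopsis is median PFS by RANO criteria.
- **Efficacy analysis (21.4).** "The Kaplan-Meier method will be used to estimate the median PFS". No test, significance level, confidence level or success rule follows. The one sentence that brings in 5.5 months speaks of the median duration and comes directly after the duration-of-response text.
- **Adjustments.** 21.4 plans modelling to match patients to the RTOG 0525 group. The synopsis (PD Parameters) says the 5.5-month benchmark will be adjusted if MGMT status differs. Neither is tied to a test.
- **Design (10.1).** "This will be an open label, uncontrolled Phase 1b/2 trial in patients with newly diagnosed GBM".
- **Effect size (10.5).** "the study is powered to detect a median PFS of approximately 8 months", which is not the effect in 21.2.

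**The concern.** The power statement and the analysis section do not describe the same analysis. Power belongs to a test, and 21.4 contains only an estimator. An ordinary log-rank test compares two groups, and here there is one. A one-sample version needs a null survival curve and a variance form, and the plan gives neither.

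That leaves several quite different analyses open: a bare comparison of the median with 5.5, a confidence limit for the median, a one-sample log-rank test, or a comparison with matched historical patients. They differ widely in type I error and power. In an open-label single-arm trial, the choice could be made after the data have been seen. Because the sentence containing 5.5 months refers to a median duration, even the quantity to be compared is unclear.

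**Working it through.** **Inputs.** From 21.2: one-sided alpha 0.10 (z = 1.2816), power 80% (z = 0.8416), 22 events in 31 patients, about 44 patients in all, null median 5.5 months. Effects: hazard ratio (HR) 0.50 from 21.2, which is 5.5/0.50 = 11 months if PFS is exponential; and about 8 months from 10.5, which is HR 5.5/8 = 0.6875. A median 50% longer would be 8.25 months, HR 0.667.

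**The plan's own figure.** At HR 0.50, no standard formula gives 22 events.

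- Two-sample 1:1 (Schoenfeld): 4 × (1.2816 + 0.8416)² / (ln 0.5)² = 4 × 4.508 / 0.4805 = 37.5, so 38. Freedman's formula gives 41.
- One-sample log-rank: HR × (1.2816 + 0.8416√HR)² / (1 − HR)² = 0.5 × 3.522 / 0.25 = 7.0. Other one-sample forms give about 7 to 13.
- At HR 0.667 the one-sample log-rank formula gives 0.667 × 3.876 / 0.1111 = 23.3, and a square-root version gives 22.3. At 8 months they give 27.6 and 26.5.

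So 22 events fits a one-sample log-rank calculation for a median about 50% longer. It does not fit a 50% hazard reduction. The step to 44 patients does follow: 31/0.70 = 44.3.

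**Median-based test, large-sample form.** With exponential PFS and no censoring, SE(log median) = 1/(ln 2 × √n), so power = Φ(|ln HR| × ln 2 × √n − 1.2816).

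- n = 31, HR 0.50: Φ(0.4805 × 5.568 − 1.2816) = Φ(1.39) = 92%
- n = 31, HR 0.667: 61%
- n = 31, HR 0.6875: Φ(0.3747 × 0.6931 × 5.568 − 1.2816) = Φ(0.16) = 57%
- n = 44: 97%, 72% and 67% in the same order

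**Simulation with censoring.** 6,000 trials per setting, exponential PFS, uniform 18-month accrual. Analysis is at the 22nd event (n = 31) or the 31st (n = 44; 44 × 22/31 = 31.2). The one-sample log-rank test uses Z = (E − O)/√E. The median test rejects when the one-sided 90% lower limit exceeds 5.5 months (log-log form).

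| True median (HR) | n / events | One-sample log-rank | Median-limit test | Median > 5.5 only |
|---|---|---|---|---|
| 5.5 (1.00) | 31 / 22 | 7.9% | 8.2% | 50.8% |
| 5.5 (1.00) | 44 / 31 | 8.1% | 8.7% | 50.2% |
| 11 (0.50) | 31 / 22 | 96.1% | 82.6% | 99.2% |
| 11 (0.50) | 44 / 31 | 98.8% | 93.4% | 99.8% |
| 8.25 (0.667) | 31 / 22 | 70.5% | 51.8% | 92.5% |
| 8.25 (0.667) | 44 / 31 | 81.9% | 65.9% | 96.4% |
| 8 (0.6875) | 31 / 22 | 65.3% | 47.9% | 90.7% |
| 8 (0.6875) | 44 / 31 | 76.3% | 61.4% | 94.7% |

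The first two rows are type I error; the rest are power. With 9-month accrual and n = 31, the median-limit test has 46%, 51% and 82% at 8, 8.25 and 11 months, and the one-sample log-rank test 64%, 70% and 96%. An untransformed limit raises the n = 31 median-test figures to 59%, 63% and 90%, but its type I error is then 11.3%, above the stated 10%.

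**The case against.** The strongest reply is that section 21 can be read as a whole. 21.2 introduces the log-rank test expressly for the primary PFS endpoint, so the log-rank test would be the inference and the Kaplan-Meier median the reported summary. That is a fair reading, and it is the arrangement proposed below. But it leaves open the one-sample or two-sample form, the null curve, the variance and the effect of the MGMT adjustment. Matching to RTOG 0525 could even mean a two-sample comparison if patient-level historical data were available, and the plan does not say.

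A reader might infer that the analysis in 21.4 lacks the stated power. The documents do not support that. 21.4 defines no test, so its power is undefined rather than low. At the hazard ratio actually written in 21.2, a median-limit test still has about 83–93%. The low figures arise only near 8 months, where the one-sample log-rank test with 22 events also misses 80%. Part of that shortfall comes from the conflict over effect size, not from the choice of test.

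A reader might also infer that the trial will declare success whenever the median exceeds 5.5 months. No section states that rule. The 50% error rate is what a literal comparison of medians would carry, not a rule the plan has adopted.

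**Conclusion.** The point holds as a gap between the power statement and the analysis section. The primary test and decision rule are not stated in 21.4, and the test named in 21.2 cannot be applied to a single arm without further definition. The readings left open matter:

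- A point-estimate comparison has about 50% type I error against the stated 10%.
- A median-limit test keeps 80% power at HR 0.50. At 8 to 8.25 months it gives up about 15 to 19 percentage points to the one-sample log-rank test (log-log limits; about 7 points with untransformed limits at n = 31, at the price of inflated type I error).

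These sizes assume exponential PFS, uniform accrual over 9 or 18 months, analysis at 22 or 31 events, and a historical median treated as known. None of these assumptions is in the documents except the 22 events and the approximate 18-month enrolment in 10.5.

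**What to change.** In 21.4:

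1. Name the primary PFS test: a one-sample log-rank test of observed versus expected events at one-sided 0.10. Specify the null curve with median 5.5 months, or that benchmark after an MGMT adjustment whose method is written down before the analysis.
2. State the population (the modified ITT population of 21.3) and the number of events that triggers the analysis.
3. Report the Kaplan-Meier median PFS with an 80% confidence interval as the estimate, not the decision rule.
4. Correct the median-duration sentence so that it refers to PFS.
5. Say how the matching to RTOG 0525 relates to the primary test.

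In 21.2, the synopsis and 10.5, choose one effect size (a 50% hazard reduction or a median of about 8 months) and restate events and power for the named test. Naming the test does not secure 80% at 8 months with 22 events: simulated power there is about 64–65% with 31 patients, and about 76% with 44 patients and 31 events.

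Naming the test costs only wording, provided it is done before the analysis. If about 8 months is the target and 80% power is kept, more events are needed.

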Study Procedures	
After providing informed consent, patients will undergo screening for eligibility to participate in the study. Screening will start within 3 weeks prior to PLX3397 dosing. Following recovery from surgical resection, patients who meet inclusion/exclusion criteria will start study drug on the morning of any Monday through Friday (Cycle 1 Day 1; C1D1). This visit should occur between 3 weeks and 5 weeks after surgery. Patients will continue to dose study drug twice daily either 7 days/week or 5 days/week (Monday through Friday) and return to the clinic for evaluation on C1D8, the day they initiate radiation therapy plus temozolomide.
 
For the Phase 1b portion of the study, a blood sample will be obtained pre-dose on C1D1 for the baseline PK. On C1D8 and on C1D15, blood samples will be obtained pre-dose and 1, 2, 4, and 6 hours post-dose to estimate PLX3397 PK. Patients will return to the clinic on Cycle 2 Day 1 (C2D1) for evaluation. If PLX3397 has been well tolerated and there has been no clinical evidence of disease progression, continued dosing will be permitted. Patients will be monitored for response and disease progression with MRI brain scans every 2 cycles, with the brain scan obtained approximately 3-4 weeks after the completion of RT serving as the baseline scan for determination of progression.
 
For Phase 1b PLX3397 dose and schedule cohorts and escalation, see Study Design (above.)
 
For the Phase 2 portion of the study, patients will be treated with PLX3397 at the RP2D level.
 
For both phases, patients will be monitored throughout the study for adverse reactions to the study drug and/or study procedures.
 
Hematology assessments (i.e., CBC, differential count, and platelet count) will be performed weekly starting with C1D1 and continuing through the first week of the Recovery Period (RPD8). Serum chemistry assessments will be performed at Screening, C1D1, C1D15, C2D1, and C2D22 (completion of RT). For the adjuvant treatment period, assessments will be made on the day of treatment initiation (C3D1), C3D22, and D22 of each subsequent cycle, and at study completion or upon early withdrawal. A serum pregnancy test will be completed at Screening for applicable patients.
 
Blood pressure, respiratory rate, pulse rate and temperature will be measured at each study visit. A standard 12-lead electrocardiogram (ECG) will be performed for each patient at Screening, C1D1, C2D1, and study completion.
 
A complete physical examination will be performed for each patient at Screening. A neurological exam and a symptom-directed physical exam will be completed on each subsequent visit while continuing study therapy, and at study completion or upon early withdrawal. Patients will also complete the MD Anderson Symptom Inventory-Brain Tumor Module at the time points noted in the Trial Flow Chart, and Karnofsky performance status will be recorded as noted.
 
A surgical paraffin tumor block (or at least 20 unstained slides) will be identified during Screening for subsequent shipment to the central pathologist. Blood samples for circulating CSF-1, biomarkers of kinase inhibition and myeloid cell recruitment will be obtained pre-dose on C1D1, C1D8, C2D1, and C3D1. CD14/16 mononuclear cell counts will be obtained pre-dose on C1D1 and C1D8.
 
Commencing on 01 October 2017, patient visits, clinical laboratory testing, and MRI brain scans will be performed approximately every 12 weeks (please refer to the TRIAL FLOW CHART – Phase 2 for details).

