### 13.13.2 Dose-Limiting Toxicities

Dose-limiting toxicities will be assessed using CTCAEv4 grading criteria. During the Phase 1b portion of the study, the DLT window will consist of 11 weeks (1 week PLX3397 run-in, 6 weeks of PLX3397 in combination with RT/temozolomide, and 4 weeks of post-RT recovery). The following will be considered DLTs:

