Additional secondary analysis of efficacy will include patient-specific biomathematical modeling of tumor growth (Baldock 2013) to allow quantification of the degree of deflection of the tumor off of its growth curve related to the therapy (Neal 2013a; Neal 2013b; Adair 2014). The patient-specific model will be tuned to the pre-treatment MRIs. The degree of deflection of the tumor off of its growth curve will be measured as Days Gained and as Radial Treatment Response as in (Neal 2013a; Neal 2013b; Adair 2014). Briefly, patient-specific simulations of predicted tumor growth will be compared with followup MRIs in terms of a temporal delay of imageable tumor growth (Days Gained) or as a delay of tumor growth in terms of size (Radial Treatment Response). These metrics will be correlated with PFS and OS through correlative and Kaplan-Meier analyses to connect treatment response with outcomes. In addition, relationships between treatment response, PFS, PD biomarkers, and tissue prognostic markers will be explored.

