- d) Stable non-enhancing (T2/FLAIR) lesions on same or lower dose of corticosteroids compared to baseline scan. In the event that the corticosteroid dose has been increased, the last scan considered to show stable disease will be the scan obtained when the corticosteroid dose was equivalent to the baseline dose.
- e) Stable clinically.

**Progressive Disease** (defined by any of the following):

- a) >25% increase in sum of the products of perpendicular diameters (bi-dimensional measurements) of enhancing lesions (over baseline if no decrease) on stable or increasing doses of corticosteroids. and/or
- b) Significant increase in T2/FLAIR non-enhancing lesion on stable or increasing doses of corticosteroids compared to baseline scan or best response following initiation of therapy, not due to co-morbid events (radiation therapy, demyelination, ischemic injury, infection, seizures, postoperative changes, or other treatment effects).
- c) Any new lesion.
- d) Clear clinical deterioration not attributable to other causes apart from the tumor (e.g., seizures, medication side effects, complications of therapy, cerebrovascular events, infection, etc.). The definition of clinical deterioration is left to the discretion of the treating physician, but it is recommended that a decrease in 20% of KPS or from any baseline to 50% or less be considered, unless attributable to comorbid events.
- e) Failure to return for evaluation due to death or deteriorating condition.

**Assessment of Response** (Efficacy)

Timing of the Evaluation of Response: Assessment of response will begin with the previous MRI. All scans are to be compared to the smallest measurement scan to date.

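### Section 21.4 fixes neither the scan that supplies Days Gained nor a landmark, so an association with PFS can arise by construction

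*Combined protocol and SAP*

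**What the plan says.** Section 21.4 lists the modelling analysis as an additional secondary analysis of efficacy. The growth model uses scans from before treatment: "The patient-specific model will be tuned to the pre-treatment MRIs". The on-treatment information comes from later scans: "patient-specific simulations of predicted tumor growth will be compared with followup MRIs". The results are Days Gained (a delay in time) and Radial Treatment Response (a delay in size). The plan then says: "These metrics will be correlated with PFS and OS through correlative and Kaplan-Meier analyses to connect treatment response with outcomes".

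The same section defines PFS as the "number of days from the first day of treatment (C1D1) to the date of the first documented disease progression", or to death if that comes first.

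The Synopsis (Study Procedures) describes MRI monitoring "with the brain scan obtained approximately 3-4 weeks after the completion of RT serving as the baseline scan for determination of progression". Later scans fall at the end of even-numbered cycles (Section 13.9), about every 8 weeks (Section 13.12). From 01 October 2017 the interval is about 12 weeks (Section 13.10). Attachment 3 counts as progression, among other criteria, a ">25% increase in sum of the products of perpendicular diameters", and compares each scan with the smallest one so far.

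The plan does not name the scan used for the metric. It gives no landmark, no time-dependent method, no cut-point for the Kaplan-Meier groups, and no rule for patients who progress or die at or before the metric scan.

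**The concern.** Only one series of on-treatment MRIs is planned, and it has two uses: it supplies the metric and it dates progression. If the metric is read from a scan that can also show progression, a patient whose tumour has grown on that scan gets a low Days Gained and an early PFS event from the same image. If the metric is the best, last or mean value over all scans up to progression, patients who stay progression-free longer also contribute later scans, and Days Gained rises with elapsed time. Either way the Kaplan-Meier curves separate without the metric predicting anything.

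At stake is the reading of a stated secondary efficacy analysis in about 44 patients with no control arm. A wide separation by Days Gained would look like evidence that response on the model carries over to outcome, and the planned analysis could not distinguish that from overlap.

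**Working it through.** The plan gives no figure for this analysis, so there is nothing to reproduce. The check sets out the scan calendar and then asks how often a metric with no predictive value would look significant.

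**Calendar**
- The time from C1D1 to C3D1 is "1 week PLX3397 run-in, 6 weeks of PLX3397 in combination with RT/temozolomide, and 4 weeks of post-RT recovery" (Section 13.13.2): 1 + 6 + 4 = 11 weeks, so C3D1 is day 11 × 7 + 1 = 78.
- The first post-baseline scan at C4D22 is day 78 + 28 + 21 = 127, or 127/30.44 = 4.17 months. With 8-week spacing from C3D1 it is week 19.
- A 25% increase in the product of diameters is √1.25 = 1.118, about 11.8% in radius.

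**Null models** (all growth parameters are assumptions; none is in the documents)
- Model A: 44 patients, 8-weekly scans, independent log-area growth N(0.10, 0.25) per interval, progression if growth exceeds log 1.25. P(progression per interval) = P(Z > (0.223 − 0.10)/0.25) = 0.31. The metric is the growth in the first interval, split at the median.
- Model B: scans at weeks 11, 19, 27 and so on, with log-radius a random walk from week 11 (8-week drift 0 to 0.05, SD 0.08-0.12). Progression is judged against the smallest scan from week 11 on. Death hazard is 0.004-0.014 per week and measurement error SD 0-0.04. Days Gained = scan week − (observed radius − starting radius)/patient velocity, with velocity median 0.35 mm/week (log-SD 0.5) and radius median 15 mm. Median PFS came out at 5.5-7.9 months, close to the plan's 5.5 (Section 21.2) and about 8 (Section 10.5).

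**Share of null trials significant at two-sided 5%, 44 patients, PFS from C1D1**

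| Scan supplying the metric | Log-rank | Spearman | Apparent HR, high vs low |
|---|---|---|---|
| C3D1 only, used purely as progression baseline (B) | 4-6% | 5-6% | 0.99-1.05 |
| First post-baseline, week 19 (B) | 13-26% | 22-47% | 0.57-0.71 |
| First post-baseline, metric equal to first-interval growth (A) | 72-77% over repeated runs | – | – |
| Best, last or mean up to progression (B) | 90-100% | 94-100% in the tabulated settings | 0.07-0.25 |
| C3D1, progression also callable on it against the postoperative scan (B variant) | 47% | 86% | 0.47 |

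Variations on Model A at the first post-baseline scan:
- Adding change before the C3D1 baseline, with velocity scatter, deaths or both in the various settings: 25-42%. One setting with progression judged against the smallest scan gave 48%.
- Fewer patients progressing at that scan (13-20%): 21-36%.
- Progression judged against the smallest scan, without the added pre-baseline change: 41-93%.

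With 31 patients, Model B gives 16% (log-rank) and 29% (Spearman) at week 19, and 97-100% for best, last or mean.

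**With a landmark** (metric and time origin at the first post-baseline scan, patients progression-free after it)
- Model A: 5.3-5.5%.
- Model B: log-rank 5.5-7.4%, Spearman 5-6%.
- Model B variant with progression callable at C3D1: log-rank 6.4% and Spearman 7.3%, against 59% and 95% for the same week-19 metric without the landmark.
- Model A with progression judged against the smallest scan: 10-14%. The excess is expected, because size at the landmark relative to the smallest scan then carries real information about crossing the threshold later.

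**Source of the bias.** The C1D1 origin alone adds a constant of about 11 weeks before the C3D1 scan, and the first table row shows no artefact with PFS still counted from C1D1. The inflation comes from keeping events that occur at or before the metric scan, or from letting the date of the metric scan move with PFS.

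**The case against.** A reader might infer that an association must appear whatever Days Gained predicts, or that the metric simply measures its own definition. The documents do not support that, for four reasons.

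- The scan is unstated. The model is tuned to pre-treatment MRIs, so the C3D1 scan can supply Days Gained, and the Synopsis makes that scan the baseline for progression. On that reading the error rate stays at 4-6%.
- Days Gained is not identical to the growth that defines progression. It also reflects change before C3D1 and each patient's own growth velocity. Rates of 72-77% arise when the two are set equal; they fall to 13-26% when Days Gained is modelled from its description.
- PFS events also include death, new lesions, T2/FLAIR increase and clinical deterioration (Section 21.4, Attachment 3), which loosens the overlap.
- Section 21.4 measures the metrics as in cited modelling studies, which may fix a scan or a landmark. They cannot be checked here.

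It can also be said that this is a secondary correlation with no alpha, cut-point or decision attached.

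These points limit the claim but do not remove it. The plan does not commit to the C3D1 reading, and its reference to follow-up MRIs in the plural permits the others. The C3D1 reading also needs that scan to be the baseline only. Attachment 3 starts response assessment from the previous MRI, which may let the C3D1 scan be judged against the postoperative one; the rate at C3D1 is then 47%.

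**Conclusion.** The concern holds in a limited form. Because Section 21.4 names no scan and sets no landmark, an association between Days Gained or Radial Treatment Response and PFS can arise by construction. Under the assumed null models the nominal 5% log-rank is significant in roughly 13-77% of trials at the first post-baseline scan (up to 93% in one family of settings with progression judged against the smallest scan). It is significant in 90-100% with the best, last or mean scan. It stays near 5% only if the metric is read once at C3D1 and that scan is solely the progression baseline.

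The ranges rest on assumed growth, velocity, death and measurement-error parameters, and no single value in them should be quoted as the trial's error rate. The documents do not support blaming the C1D1 origin by itself. Nor do they support extending the shared-scan argument to OS, where only the need to survive to the scan applies. The primary PFS comparison is not affected. This is an inexpensive improvement to a secondary analysis.

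**What to change.** In Section 21.4:
- Name one scan for both metrics, either C3D1 or the first post-baseline scan (C4D22).
- For PFS, include only patients progression-free after that scan; for OS, include patients alive at it.
- Count PFS and OS from that scan, or enter the metric as a time-dependent covariate.
- State how many patients are left out because they progressed, died or had no scan.

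Reconcile the Synopsis and Attachment 3 on whether the C3D1 scan can itself show progression. If C3D1 is chosen for the metric, its freedom from the artefact without a landmark depends on the answer.

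The cost is SAP wording and a smaller PFS correlation. With exponential PFS and a median of 8 months, the proportion progression-free at the first post-baseline scan is 0.5^(4.17/8) = 0.697, so about 0.697 × 44 = 31 of 44 patients remain. Fewer are lost if C3D1 is used.

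### Section 21.4 links two continuous imaging metrics to censored PFS and OS through an undefined correlation and Kaplan-Meier curves with no stated cut; a Cox model from a landmark scan would use the data better at little cost

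*Combined protocol and SAP*

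**What the plan says.** Section 21.4 (Efficacy Analysis) introduces the work with "Additional secondary analysis of efficacy will include patient-specific biomathematical modeling of tumor growth". The metrics are obtained after treatment starts: "patient-specific simulations of predicted tumor growth will be compared with followup MRIs". They are expressed as a "temporal delay of imageable tumor growth (Days Gained) or as a delay of tumor growth in terms of size (Radial Treatment Response"), that is, as a number of days and as a size difference. Their link to outcome rests on one sentence: "These metrics will be correlated with PFS and OS through correlative and Kaplan-Meier analyses to connect treatment response with outcomes". The section then says only that further relationships with PFS and biomarkers will be explored.

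The same section counts PFS from C1D1 and makes it right-censored: "PFS and duration of response will be censored at the date of last evaluable tumor assessments". For survival it says "The secondary endpoint of OS will be analyzed in a similar fashion".

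For this analysis the documents give no cut-point, type of correlation, regression model, choice of scan, alpha, effect size or power. The only planned event count belongs to the primary PFS comparison in section 21.2: "22 events (death or progression) in approximately 31 patients would be required".

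**The concern.** Neither named route, taken in its ordinary sense, fits a continuous predictor and a censored outcome.

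- Kaplan-Meier estimation compares groups. Each metric must therefore be cut, which discards information, and the cut is left open.
- A Pearson or Spearman coefficient keeps the metric continuous but has no place for a censored time. Censored patients must either be dropped or have their follow-up times treated as event times.

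In a trial of 31 to 44 patients, the lost information can hide a real association between imaging response and outcome. An open cut works the other way: with two metrics and two endpoints, a search for the best-looking split can produce an association that is not there.

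**Working it through.** **The plan's own figure.** There is none to reproduce, because no power or effect size is stated for this analysis. The 22 events and 31 patients of section 21.2, and the total of about 44, are used below only to set the scale. Censoring at 22 events is (31 − 22)/31 = 29%, or (44 − 22)/44 = 50%.

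**Analytic check.** With D events and log hazard ratio β per SD, approximate two-sided 5% power for Cox regression on the continuous metric is Φ(√D·β − 1.96). A split at the median keeps 2/π = 0.64 of the information for a normally distributed metric. Take D = 22 and assume β = 0.5:

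- Cox: √22 × 0.5 − 1.96 = 2.345 − 1.960 = 0.385, so power is 65%.
- Median split: √(22 × 0.637) × 0.5 − 1.96 = 1.871 − 1.960 = −0.089, so power is 46%.

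The loss is about 19 points.

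**Simulation at the same effect.** Assumptions: standard normal metric; exponential PFS with an 8-month median at the mean metric; log HR 0.5 per SD; uniform accrual over 5 or 18 months; cut-off at the stated event; two-sided 0.05; 2,000 replicates per setting. Power in %:

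| Setting | Cox, continuous | Log-rank, median split | Spearman, censoring ignored | Spearman, events only |
|---|---|---|---|---|
| n=31, 22 events | 57–58 | 40–41 | 44–48 | 14 |
| n=44, 22 events | 59–61 | 40 | 34–44 | 9–11 |
| n=44, 35 events | 77 | 56–58 | 66–67 | 25–28 |

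Absolute power is a few points below the analytic value, but the gap between Cox and the median split is about the same. Against Cox, the median split loses about 17–21 points and Spearman ignoring censoring about 9–25.

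**How the loss moves with the assumed effect.** A second simulation (n=31, 29% censored by independent uniform censoring, 1,500 replicates, Monte Carlo SE about 1.3 points) gives these points lost against Cox:

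| HR per SD | 1.25 | 1.5 | 1.75 | 2.0 | 2.5 |
|---|---|---|---|---|---|
| Cox power (%) | 17 | 43 | 67 | 85 | 96 |
| Median split | 3 | 14 | 22 | 23 | 15 |
| Spearman, censoring ignored | 3 | 11 | 14 | 14 | 6 |
| 80/20 cut | 10 | 26 | 40 | 48 | 46 |
| Spearman, events only | 10 | 33 | 48 | 60 | 53 |

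The loss is small when no method has power and shrinks again as every method nears 100%. At n=44, 35 events and log HR 0.9, Cox has 99.4% and Spearman ignoring censoring 98.2%. For the median split at HR 2.5 the analytic loss is 6 points at 22 events and 2 at 31 events; the simulation above still shows 15.

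**OS.** No event count is given, so censoring must be assumed. At n=44 over the same hazard ratios, 50% censoring costs the median split 5–23 points and Spearman ignoring censoring 4–20. At 70% censoring the losses are 4–22 and 5–35.

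**False positives.** With no association, fixed cuts from 50/50 to 80/20 and both uses of the correlation rejected in about 4–6% of replicates. Taking the best-looking cut between the 20th and 80th percentiles raised a nominal 5% error to about 26–32% for one metric and one endpoint.

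**Timing.** PFS runs from C1D1. After screening, the Phase 2 flow chart schedules the next MRI at C3D1, which is 1 + 6 + 4 = 11 weeks later. Patients who progress or die before the scan used have no metric. An analysis that counts time from C1D1 by a value measured later credits patients with time they had to survive in order to be measured.

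**The case against.** The strongest reply is that the plan is unspecific here rather than wrong. The protocol uses the word correlative as a general label (correlative imaging is a listed secondary endpoint), so a censoring-aware measure, or even Cox regression, is not excluded. This stands. A reader might infer that section 21.4 commits to a method that mishandles censoring; the text does not go that far. What it does is leave the method and the cut open.

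A reader might also infer a loss of up to 50 points, or of at least 5 points whatever is done. Neither is supported. Losses near 50 need censored patients to be dropped, or a cut near 80/20, and the documents propose neither. At the other end, losses of 1 to 3 points occur at very strong or weak effects. Every size here rests on an assumed hazard ratio.

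The 50% censoring figure is also a high case for PFS. Section 21.2 pairs 22 events with 31 patients and makes neither number a cut-off for this analysis, while scans and survival follow-up continue.

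A Cox model with time counted from C1D1 would not be sound either, because the metrics are measured later. That is correct, and the fix allows for it. The named correlation and Kaplan-Meier analyses share the problem. For the same reason the simulations, which treat the metric as known at time zero for everyone, show relative efficiency and do not forecast the power of a landmark analysis.

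**Conclusion.** The point holds as a low-cost improvement to an additional secondary analysis. Two continuous metrics are to be related to censored endpoints with no cut, no defined correlation and no regression model.

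If the log HR is 0.5 per SD, with 22 events in 31 to 44 patients and two-sided 0.05, Cox regression on the continuous metric has about 58–60% power. That compares with about 40% for a median split and 34–48% for a Spearman correlation that ignores censoring. These sizes also assume a normally distributed metric, a log-linear effect and independent censoring.

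A cut chosen after seeing the data would inflate a nominal 5% error to about 26–32%. With a fixed cut in the 50/50 to 80/20 range, the harm is lost power and not excess false positives.

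A reader might take this as a threat to the trial's main result. It is not: no alpha, power or decision is attached to this analysis, and the primary PFS comparison does not use it.

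**What to change.** In section 21.4, replace the sentence on correlating the metrics with PFS and OS by wording such as:

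> Each metric, taken from one prespecified follow-up scan, will be entered as a continuous covariate in a Cox model for PFS and for OS, with time counted from that scan among patients still at risk. The hazard ratio per SD and its 95% CI will be reported. Kaplan-Meier curves from the same landmark, split at the sample median, will be shown for display only.

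Entering the metric as a time-dependent covariate is an acceptable alternative to the landmark. The scan should be named before outcome data are examined.

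The cost is a few lines of text and one standard model per metric and endpoint, with no new patients, visits or scans. There are two small downsides. The model assumes a log-linear effect, which residuals can check. Patients with an event before the landmark are excluded, and their number should be reported.
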